PR-NV16099	Version C	Page 19 of 144	Medtronic
Per-protocol (PP) population		Per-protocol population is ITT sub	jects excluding the
		 Subjects with use of more device other than Pipelin Embolization Device with (e.g., adjunctive coils) du 	e™ Vantage Shield Technology™
		 Subjects with failed impla device at index procedure 	
		 Subjects assessed as mF independent and certified 	
Principal Investigator (PI)		Qualified person responsible for c clinical investigation at an investig 14155:2011 3.33)	-
Procedure		The primary study procedure invo of the Pipeline™ Vantage Emboliza Shield Technology™ at Day 0.	
Procedural Technical Success		Procedural Technical Success is m of successful implantation of the s the study index procedure at the t of the number of devices deployed the target site.	tudy device during arget site regardless
Recurrence		Aneurysm achieving complete occ Roy 1) followed by incomplete occ Roy 2 or 3) at follow-up exam, as a	lusion (Raymond
Serious Adverse Device Effect (SADE	:)	An adverse device effect that has the consequences characteristic o event. (ISO 14155:20113.36)	-
Serious Adverse Event (SAE)		 An adverse event that: a) Led to death, b) Led to serious deterioration subject, that either resulted 1. A life-threatening illnes 2. A permanent impairment structure or a body fundament 	in ss or injury, or ent of a body

Medtronic Controlled Information

056-F275, v A Clinical Investigation Plan Template

PR-NV16099	Version C	Page 20 of 144 Mectronic
		 In-subject or prolonged hospitalization, or Medical or surgical intervention to prevent life-threatening illness or injury or permanent impairment to a body structure or a body function,
		 c) Led to fetal distress, fetal death or a congenital abnormality or birth defect (ISO 14155:2011 3.37) Note: Planned hospitalization for a pre-existing condition, or a procedure required by the CIP, without serious deterioration in health, is not considered a SAE.
Stroke		Stroke is defined as a focal neurological deficit of presumed vascular origin persisting ≥24 hours from symptom onset and a neuro-imaging study or other quantitative study that does not indicate a different etiology. The 24-hour criterion is excluded if the subject undergoes cerebrovascular surgery or dies during the first 24 hours.
		 The definition includes: Subjects presenting with clinical signs and symptoms suggestive of SAH, intracerebral hemorrhage, or cerebral infarction.

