The primary objective of the SHIELD Study was to assess the outcomes of the Pipeline[™] Shield device in subjects undergoing treatment for intracranial aneurysms in a real-world, post-market setting. The SHIELD study, conducted in 21 sites outside the United States (OUS), which included European Union (EU), Australia and Israel, prospectively consented 205 subjects and attempted to treat a total of 204 target aneurysms in 204 subjects. The aneurysms were located in the parent arteries of the ICA (segments C1-C7) (76.0%, 155/204), MCA (7.8%, 16/204), Vertebral Artery (6.4%, 13/204), Anterior Communicating Artery (5.9%, 12/204), and ACA (3.9%, 8/204). The majority of aneurysms were located in the ICA (76.0%, 155/204), most of which were located in C6 (ophthalmic segment, 41.2%, 84/204) and C7 (communicating segment, 19.1%, 39/204). Of the 204 target aneurysms, 50.0% (102/204) were small (< 7 mm), 33.8% (69/204) were medium (7-12 mm), 13.7% (28/204) were large (13-24 mm), and 2.5% (5/204) were giant (≥ 25 mm). The majority of target aneurysms (81.4%, 166/204) were never ruptured at the time of entry into the study, while previously ruptured target aneurysms were reported as acutely ruptured (<30 days) in 1.5% (3/204) and as previously ruptured > 30 days in 16.7% (34/204); rupture status was not reported in the remaining 0.5% (1/204) of target aneurysms. Device deployment success on a subject level was observed in 98.0% (200/204) of subjects.

In the SHIELD Study, follow-up visits were not required by the Clinical Study Protocol and only conducted per standard of care at the investigational site. In the study population, 87.3% (178/204) subjects returned for the 30-day follow-up visit, 81.4% (166/204) subjects returned for the 3 month follow-up visit, 91.2% (186/204) subjects returned for the 6 month follow-up visit, and 83.8% (171/204) subjects returned for the 1 year follow-up visit. Complete aneurysm occlusion without significant parent artery stenosis (\leq 50%) or retreatment of the target aneurysm 1-year post-procedure (primary effectiveness endpoint) occurred in 71.67% of subjects. A total of 75.0% (141/188) subjects had complete target aneurysm occlusion, 0.0% (0/204) subjects had aneurysm recurrence and 2.0% (4/200) subjects and residual aneurysm was seen in 20.2% (38/188) of subjects. Through 1-year follow-up, majority of subjects (98.94%, 186/188) did not have significant stenosis, defined as >50% stenosis of the parent artery.

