5.1.2.1. Secondary Endpoint(s)

The following will be assessed for the effectiveness outcome measures:

- 1. Incidence of successful device implantation at the target site
- 2. Incidence of complete aneurysm occlusion (Raymond Roy Class 1) at 1- and 3-years postprocedure
- 3. Incidence of target aneurysm recurrence at 1- and 3-years post-procedure

For the purposes of this study protocol, successful device implantation will be presented in terms of Procedural Technical Success and Device Technical Success. Procedure technical success is measured by the rate of successful implantation of the study device during the study index procedure at the target site regardless of the number of devices deployed and implanted at the target site. Device technical success is measured by the rate of successful study device implantation at the target site with the total number of devices attempted to be deployed.

Successful device implantation and retreatment will be site reported. Aneurysm occlusion class, recurrence, and parent artery stenosis will be assessed by the independent Imaging Core Lab.

The following will be assessed for the secondary safety endpoints:

- 1. Incidence of major stroke in the territory supplied by the treated artery or neurological death at 2- and 3-years post-procedure
- 2. Incidence of major stroke in the territory supplied by the treated artery or neurological death at 30 days post-procedure
- Incidence of delayed intraparenchymal hemorrhage >30 days post-procedure through 1-year post-procedure
- Incidence of subjects with disabling strokes that have a mRS decline to a score of 3 or more (mRS ≥ 3) due to a stroke-related cause assessed at a minimum of 90 days post-stroke event at 1 year, 2 year, and 3 year post-procedure

The events comprising the safety endpoints will be adjudicated by the independent CEC.

PR-NV16099

Version C

Page 47 of 144

6. Study Design

The study is a prospective, global, multi-center, single-arm IDE clinical study evaluating the performance of the Pipeline[™] Vantage Device. The Pipeline[™] Vantage Device is investigational in the United States and Canada.

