- Pregnancy test (Pregnancy test (serum or urine) only required for females of childbearing potential. Females who are surgically sterile or post-menopausal are not required to take a pregnancy test). At the 2-year follow-up, pregnancy test is only required for female subjects of childbearing potential that are undergoing DSA imaging.
- Record protocol specified medications
- Record concomitant medications
- If aneurysm is not occluded at 1 year or subsequent follow-up visits (per core lab assessment), DSA must be performed at 2-year follow-up. If child bearing potential woman becomes pregnant during the study, subject may obtain MRA without contrast instead of DSA.
- mRS assessment to be carried out by a certified independent assessor at site

ADVANCE Clinica	I Investigation Plan		
PR-NV16099	Version C	Page 85 of 144	Medtronic

- Full neurological exam and assessment of aneurysm symptoms (new, worsened, improved, stable)
- Assessment of Adverse events of interest

9.9.5. 3-Year

At 3-year post-procedure (±56 days), the following study assessments shall be performed and recorded in the eCRFs:

- Pregnancy test (Pregnancy test (serum or urine) only required for females of childbearing potential. Females who are surgically sterile or post-menopausal are not required to take a pregnancy test). At the 3-year follow-up, pregnancy test is only required for female subjects of childbearing potential that are undergoing DSA imaging.
- Record protocol specified medications
- Record concomitant medications
- If aneurysm is not occluded at 1 year and subsequent follow-up visits (per core lab assessment), DSA must be performed at 3- year follow-up. Subjects with aneurysm occluded at 1 year and subsequent follow-up visits (per core lab assessment) to undergo DSA, if performed per standard of care; if DSA not collected per standard of care, subject must undergo CTA imaging. Under certain conditions, MRA imaging may be obtained instead of a DSA or CTA imaging e.g., subjects with iodine allergies, borderline renal function, pregnancy, or concerns over excessive radiation. The justification for using MRA over DSA or CTA should be captured in the case report form. Precaution: DSA or CTA imaging are preferred over MRA imaging due to the risk of reduced image quality (artifact) when attempting to visualize near or inside the implanted device with MRA imaging.
- mRS assessment to be carried out by a certified independent assessor at site

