13.3. Analysis Populations

To ensure adequate representation patient with large and giant aneurysms must be enrolled. All primary and secondary endpoints will be analyzed both on an ITT and PP basis. All summarizations and tabulations will be conducted on the ITT population, defined below.

Intent-To-Treat Population: All subjects who were consented and in whom deployment of the Pipeline[™] Vantage Device was attempted (i.e., puncture at the arterial access site), independent of the procedure being completed successfully.

Subject will not be considered part of the ITT population if the puncture at the arterial access site for deployment of Pipeline[™] Vantage Device was not successful. If the puncture at the arterial access site for deployment of Pipeline[™] Vantage Device was successful, the subject will be considered part of the ITT population. Consented subjects who withdraw consent prior to undergoing the study procedure or are found not to meet the inclusion/exclusion criteria prior to undergoing the study procedure, will not be included in the ITT population.

The ITT population will be the primary population for all analyses.

PR-NV16099

The PP population defined below will be used for sensitivity analyses and to provide outcomes for subjects with observed data.

Per-Protocol Population: Per-protocol population is ITT subjects excluding the following subjects:

- Subjects with use of more than 1 treatment device (e.g., coils) other than Pipeline[™] Vantage device during index procedure
- Subjects with failed implantation of study device at index procedure
- Subjects assessed as mRS ≥3 at baseline by independent and certified assessors

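### Recurrence presupposes an earlier complete occlusion, but the plan tabulates it on populations that keep never-occluded subjects, so the percentage understates loss of occlusion

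*Combined protocol and SAP*

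**What the plan says.** Section 5.1.2.1 lists "Incidence of target aneurysm recurrence at 1- and 3-years post-procedure" as the third secondary effectiveness measure, and Section 13.8.3 repeats it. The glossary (Section 2) sets two conditions. The entry opens with "Aneurysm achieving complete" occlusion, that is Raymond Roy 1, and then requires incomplete occlusion, "Roy 2 or 3) at follow-up exam".

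The population rules are in Section 13.3. For the endpoints it says "All primary and secondary endpoints will be analyzed both on an ITT and PP basis". For tables, ITT alone is named as the set to use. The overall rule is "The ITT population will be the primary population for all analyses". ITT takes in everyone with a successful arterial puncture, whether or not a device was implanted. The per-protocol set removes failed implants, users of other treatment devices and subjects with baseline mRS of 3 or more. It does not remove subjects whose aneurysm never occluded.

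Section 13.8.3 adds only that secondary endpoints are summarized in frequency tables, without testing. No section limits the recurrence denominator to previously occluded subjects or says which visit establishes the earlier occlusion.

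**The concern.** The definition and the population rule do not fit together. A subject who was never occluded cannot recur, yet sits in the denominator as a non-event. The resulting percentage mixes two things: how often the device occludes, and how often occlusion is then lost. The mixture runs the wrong way, because at a given risk of losing occlusion, a device that occludes fewer aneurysms shows a lower recurrence percentage.

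Sustained occlusion is central to the protocol's case against stent-assisted coiling (Section 6.2), and low recurrence is claimed for Pipeline at the end of Section 4.2.7. The recurrence figure should therefore measure loss of occlusion.

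**Working it through.** **Plan's own figure.** The documents give no expected rate, power or interval for recurrence, so there is nothing to reproduce.

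**Who can be at risk.** Before the 1-year visit, the scheduled follow-up imaging is at the end of the procedure (Section 9.5.4) and at 180 days (Section 9.9.2). A subject whose first Class 1 reading is at 1 year cannot have a 1-year recurrence. The share occluded by 180 days is thus the closer proxy for the 1-year rate, and the share occluded by 1 year for the 3-year rate. Subjects never successfully implanted are followed only at 1 year (Section 9.9).

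**Inputs**
- N = 100 treated subjects (Section 13.2).
- x = 3 recurrences: illustrative, not in the documents.
- q = share with an earlier Class 1 reading: assumed 0.65 to 0.868. Guides: PUFs at 180 days 78/106 = 73.6% (occlusion without major stenosis); SHIELD at 1 year 141/188 = 75.0%; PREMIER at 1 year 113/138 = 81.9%; PUFs at 1 year 79/91 = 86.8%. The low end, 65%, is the lowest effectiveness rate considered for power in Section 13.2. The small PITA study lies above the range at 28/30 = 93.3%.

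**Formulas**
- ITT rate = x/N; at-risk rate = x/(Nq). Their ratio is q, so the relative understatement is 1 − q.
- Exact one-sided 97.5% upper bound with zero events in n subjects = 1 − 0.025^(1/n).

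| q | At risk (of 100) | Understatement 1 − q | 3 events | Upper bound, 0 events |
|---|---|---|---|---|
| ITT as written | 100 | – | 3/100 = 3.0% | 3.6% |
| 0.65 | 65 | 35% | 3/65 = 4.6% | 5.5% |
| 0.736 | 74 | 26% | 3/74 = 4.1% | 4.9% |
| 0.75 | 75 | 25% | 3/75 = 4.0% | 4.8% |
| 0.819 | 82 | 18% | 3/82 = 3.7% | 4.4% |
| 0.868 | 87 | 13% | 3/87 = 3.4% | 4.2% |

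At PITA's 93.3% the understatement would be 1 − 0.933 = 6.7%.

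**Earlier reports in the protocol**
- SHIELD (Section 4.2.7): "0.0% (0/204) subjects had aneurysm recurrence", although 141 of 188 read were occluded. Upper bound 1.8% for 0/204, against 2.6% for 0/141.
- PREMIER (Section 4.2.5): 0/138, although 113 of 138 were occluded. Upper bound 2.6% for 0/138, against 3.2% for 0/113.

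With no recurrences, subjects who were occluded earlier and re-imaged at 1 year should be among those occluded at 1 year. So 141 and 113 are at most the numbers at risk, and the second bound in each pair is not exaggerated.

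**The case against.** **Population is not denominator.** Section 13.3 names a population, Section 13.8.3 gives no denominator for any secondary endpoint, and Section 13.1 leaves detail to a separate SAP. This stands as a caveat: the SAP could restrict the denominator. Until it does, the ITT rule governs, and the earlier reports did not make the restriction.

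**Per-protocol analysis.** It does remove failed implants. It does not remove never-occluded subjects, so the main source of dilution remains.

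**Subjects without imaging.** A reader might infer that they are counted as recurrence-free. The documents do not establish this. Section 13.4 calls for multiple imputation of missing endpoint data in ITT, and PREMIER used 138 rather than the 141 treated. That rule brings its own difficulty: the imputation variables listed are age, gender, aneurysm diameter and location. Prior occlusion is not among them, so a never-occluded subject could be assigned a recurrence status if the rule is applied here.

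**Zero events.** PUFs, PREMIER, SHIELD and PFLEX all report no recurrence, and 0% is 0% on any denominator. This stands. Only an upper bound would change, and the plan schedules no interval for this endpoint.

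**Visibility.** Complete occlusion is reported alongside, and recurrence per treated subject is a legitimate quantity. Both are true, but neither makes the ITT percentage a measure of durability.

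**MRA at 3 years.** A reader might infer that a poor MRA image will be scored as no recurrence. Nothing says so. MRA is barred within 1 year, is allowed later only under certain conditions with a recorded reason (Section 9.9.5), and recurrence is assessed by the core lab. This is not part of the error.

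**Conclusion.** The mismatch is real and follows from the plan's own definition and population rule. The ITT percentage equals the at-risk rate multiplied by the share previously occluded, which is an understatement of about 13% to 35% for an assumed share of 65% to 87%. The shares come from earlier-generation devices, differ in visit and case mix, and in one case are a composite with stenosis.

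It would be wrong to quote the 26% obtained from the 180-day PUFs figure as the effect throughout. That is one proxy, for the 1-year rate; using 1-year occlusion of 86.8%, the 3-year effect is about 13%.

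Consequences are limited. The endpoint is secondary, descriptive and untested, no decision rule depends on it, and both primary endpoints are untouched.

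**What to change.** In Section 13.8.3, and in the SAP:

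1. Define the recurrence denominator as subjects with a core-lab Class 1 reading at an earlier exam and an evaluable later image.
2. Name the visits that can establish the earlier occlusion, separately for the 1-year and 3-year rates.
3. Report the rate with an exact binomial interval.
4. State that recurrence is not imputed for subjects without an earlier Class 1 reading.
5. Keep the percentage per ITT subject as a labelled supplement.

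Tabulating 3-year recurrence by imaging modality is an optional addition.

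The cost is a few lines of text. No new data, visits or subjects are needed. If any recurrence occurs, the headline rate will be somewhat less favourable than the ITT percentage.

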8.4. Exclusion Criteria

The subject must not meet any of the following exclusion criteria:

Imaging Criteria (Core Lab Assessed)

- 11. Subject has internal carotid artery bifurcation aneurysm.
- 12. Aneurysms that arise from the Posterior Communicating Artery (PComm).
- 13. The internal carotid artery aneurysms of the C7 segment will be excluded under the following conditions:
 - Observed fetal posterior communicating artery (PComm) (A PComm of fetal origin is defined as a small, hypoplastic, or absent P1 segment of the posterior cerebral artery (PCA) with the PComm artery supplying a majority of blood flow to the P2 and higher order segments of the PCA)
 - b. PComm overlapping with the aneurysm neck
 - c. PComm branch arising from the dome of the aneurysm
- 14. Subject has an eurysm arising from internal carotid artery but is primarily fed by posterior circulation (i.e., retrograde flow from the basilar artery) as confirmed by DSA

Clinical Criteria

- 15. Subject requires treatment of another aneurysm (with another treatment modality) within the affected territory of the target aneurysm during the study period.
- 16. Subject has received an intracranial implant (e.g. coils) in the area of the target intracranial aneurysm within the past 6 months prior to the study procedure.
- 17. Subject has had a SAH and/or target aneurysm rupture in the past 30 days prior to the study procedure.
- 18. Subject has undergone a surgery including endovascular procedures in the last 30 days prior to the study procedure.
- 19. Vessel characteristics (e.g. severe tortuosity, stenosis, morphology) that preclude safe endovascular access to the aneurysm to allow for necessary access to treat with the study device.

PR-NV16099	Version C	Page 69 of 144		Medtronic
------------	-----------	----------------	--	-----------

- 20. Aneurysm vessel characteristics (e.g., parent vessel stenosis, irregular morphology) that would preclude the device from fully conforming to the parent vessel to reduce any risk of embolic complications, re-treatment, or device movement.
- 21. Subject has active vasospasm, malignant brain tumor or vascular malformation (e.g. arteriovascular malformation).
- 22. History of major bleeding disorder (based on coagulation profile and platelet count) and/or subject presents with signs of active bleeding.
- 23. Subject requires adjunctive device use (e.g. coils) during the index procedure.

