9.5.3. Adjunctive Device Use

Adjunctive devices are defined as devices (other than the Pipeline[™] Vantage Device) that are used to treat the target aneurysm.

Adjunctive device use (e.g. coils) is not allowed during the index procedure. Subjects that will require concomitant coiling should be excluded from the study (exclusion criteria). However, previous coiling failed subjects can be included.

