9.5.6. No Treatment of an Eligible Subject with the Pipeline[™] Vantage Device

In the event that the subject was confirmed to be eligible for the study at baseline, signed informed consent, but the target intracranial aneurysm is not treated with the Pipeline[™] Vantage Device at the initially scheduled procedure, the subject may be brought in later to undergo the Pipeline[™] Vantage Device. In this case:

- In the event the subject does not meet protocol specified PRU value range (≥60 and ≤200) or TEG value range (>30% to <90%) on the day of the procedure, the procedure should be delayed (and no puncture at the arterial access site performed) until a protocol specified therapeutic range for PRU/TEG is achieved. The day of the puncture at the arterial access site is considered day 0.
- 2) In cases where PRU/TEG criteria is met and puncture at the arterial access site is performed, and the aneurysm is not able to be accessed or a study device unable to be deployed, the reasons of the inaccessibility of the aneurysm or study device failing to deploy (incomplete treatment) will be captured. Any alternate treatments if received will be captured. Such subjects will not be included in the per-protocol analysis. In cases where the subject is brought back at a later time and undergoes a second procedure with the study device, the date of the first intervention will be considered Day 0. The second intervention (if successful) will not be considered a retreatment. The subject must be brought back for the second intervention within 6 weeks of the initial attempted treatment.

PR-NV16099

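### The per-protocol rule in section 13.3 removes subjects only for two or more non-study treatment devices, although the protocol allows none, so a subject with exactly one stays in the set

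*Combined protocol and SAP*

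**What the plan says.** Section 13.3 builds the per-protocol population by taking the ITT population and removing three groups:

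- "Subjects with use of more than 1 treatment device (e.g., coils) other than" the Pipeline Vantage device during the index procedure;
- "Subjects with failed implantation of study device at index procedure";
- subjects rated mRS 3 or more "at baseline by independent and certified assessors".

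The same section makes ITT the primary population for all analyses. It assigns the per-protocol set to sensitivity analyses and to showing outcomes in subjects with observed data. It also says that every primary and secondary endpoint will be analysed on both populations.

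The rules on adjunctive devices stand elsewhere. Section 9.5.3 defines them as devices other than the study device that are used to treat the target aneurysm, and states: "Adjunctive device use (e.g. coils) is not allowed during the index procedure". It adds that subjects who will need "concomitant coiling should be excluded from the study (exclusion criteria" criteria). Exclusion criterion 23 in section 8.4 reads: "Subject requires adjunctive device use (e.g. coils) during the index procedure".

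One further per-protocol rule stands outside section 13.3. Section 9.5.6, on subjects whose aneurysm could not be reached or in whom the device could not be deployed, says: "Such subjects will not be included in the per-protocol analysis".

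**The concern.** A per-protocol set should leave out subjects whose treatment departed from the protocol in a way that bears on the endpoint. Here the permitted number of adjunctive devices is zero, but the exclusion starts at two. A subject with exactly one is a protocol violation by sections 8.4 and 9.5.3 and still counts as per protocol under section 13.3.

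The violation matters for interpretation because a coil or similar device placed in the target aneurysm could itself affect occlusion or cause a safety event. With a single arm, no control group absorbs that effect. The per-protocol occlusion and safety rates would then describe, for those subjects, the study device plus something else.

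**Working it through.** The point rests on no stated sample size, power or alpha, so the check is mainly a comparison of passages. A short illustration of size follows.

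**Step 1. Thresholds side by side** (number of non-study treatment devices at the index procedure)

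| Number used | Allowed by 9.5.3 and exclusion 23? | Removed by the first bullet of 13.3? |
|---|---|---|
| 0 | Yes | No |
| 1 | No | No |
| 2 or more | No | Yes |

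The middle row is the mismatch.

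**Step 2. Does another rule catch the middle row?**

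- The second and third bullets of 13.3 remove such a subject only if implantation failed or baseline mRS was 3 or more.
- Section 9.5.6 covers only failed access or deployment.
- Section 13.3 has no general exclusion for major deviations or eligibility violations.
- ITT keeps the subject by design, since successful arterial puncture is enough for membership.
- The endpoint definition does not catch the subject either. Effectiveness success requires no retreatment, but the glossary defines retreatment as something that happens after the primary study procedure implantation. An adjunctive device used at the index procedure itself does not naturally fall under that.

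So a subject with a successful study-device implant, baseline mRS of 2 or less and exactly one adjunctive device remains in the per-protocol set and can count as a success there.

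**Step 3. Size for one subject.** The correction takes the subject out of numerator and denominator. With x successes among n, removing one success changes the rate from x/n to (x − 1)/(n − 1). Lower bounds are exact (Clopper-Pearson) one-sided 97.5% bounds. The starting counts are assumptions: 69/100 matches the 69% that section 13.2 uses for 95% power with 100 patients, and 61/100 is the smallest count whose lower bound exceeds 50% (60/100 gives 49.7%).

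| Start | Rate, lower bound | After removing one success | Rate, lower bound | Change in rate |
|---|---|---|---|---|
| 69/100 | 69.0%, 59.0% | 68/99 | 68.7%, 58.6% | −0.3 points |
| 61/100 | 61.0%, 50.7% | 60/99 | 60.6%, 50.3% | −0.4 points |

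In both cases the lower bound stays above 50%. Starting from exactly 61/100, removing two successes gives 59/98 = 60.2% with bound 49.8%, which is below 50%.

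**Step 4. Direction.** Suppose 5 of the 100 had exactly one adjunctive device, with 69 successes overall. If all 5 were successes, removing them gives 64/95 = 67.4% (bound 57.0%). If all 5 were failures, it gives 69/95 = 72.6% (bound 62.5%). Kept as written, the rate is 69.0%. The documents give no outcome data for such subjects and no expected number of them, so the sign is open.

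**The case against.** The strongest reply is that little depends on this. ITT is primary, and adjunctive-device subjects stay in ITT however the per-protocol bullet is worded, so no primary conclusion, alpha, power or sample size moves. Adjunctive use is both an exclusion criterion and forbidden during the procedure, so cases should be rare. Given the outright ban and the example of coils, the bullet was probably meant to cover any device used in addition to the study device. Section 13.1 also promises a detailed SAP before any analysis, which could settle the wording. All of this stands as a limit on impact. It does not rescue the text: more than one device other than the study device is not the same as any, and nothing in the documents supplies the intended reading.

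A reader might also infer more than the documents support:

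- *That the retained subjects inflate the occlusion rate.* This holds only if they are successes; Step 4 shows that the reverse is possible.
- *That each such subject moves the rate by a full percentage point.* That would be the effect of recoding a success as a failure at N=100. Exclusion moves it by 0.3 to 0.4 points in the cases shown.
- *That the per-protocol set carries a pass/fail decision at 61/100, or exists to isolate the study device.* Section 13.3 gives it a sensitivity role and states no isolating purpose.
- *That the glossary has the same defect.* Its per-protocol entry is broken in the available text at the point where the count would stand, so this cannot be confirmed.

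**Conclusion.** The rule is wrong as written. Section 13.3 sets the exclusion at two or more non-study treatment devices, sections 8.4 and 9.5.3 allow none, and no other per-protocol rule removes a subject with exactly one, unless implantation failed or baseline mRS was 3 or more. The per-protocol occlusion and safety rates would therefore mix study-device and adjunctive-device effects for any such subject.

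The consequence is confined to sensitivity results, although these span all primary and secondary endpoints. It is likely to be small and its direction is unknown. Only a per-protocol result sitting exactly at the margin could change sides of 50%, and in the illustration that took two removed successes. This assessment assumes a literal reading of the bullet, about 100 subjects in the per-protocol set, and few adjunctive-device cases; the documents give no expected count.

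**What to change.** In the first per-protocol bullet of section 13.3, replace the words for more than one with *any*, so that it removes every subject in whom any treatment device other than the Pipeline Vantage device was used during the index procedure. Check the glossary definition of the per-protocol population against the new bullet and align it if it differs. Carry the same wording into the detailed SAP before data are analysed.

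The change touches only the analysis definition. Sample size, alpha, the ITT analysis and study conduct stay as they are. The downside is that the per-protocol set may lose a subject or two.
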